5.3.3. Time to Event Endpoints

Subjects who reach the end of their accrual period without experiencing the event of interest will have their event times right censored at the end of their accrual period (ie, administrative censoring). Subjects who permanently discontinue before the end of their accrual period without experiencing the event of interest will have their event times considered missing.

For the primary analysis, these missing event times will be considered as right censored (censored at random) on their last date of dosing. As sensitivity analyses, tipping point analyses will be performed where these missing event times will be multiply imputed under an assumption of censoring not at random as proposed in Atkinson et al. (2019)¹ (see [Appendix 6](#)).

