### **Lost to follow-up:**

All reasonable efforts must be made to locate subjects to determine and report their ongoing status. This includes follow-up with persons authorized by the subject as noted above. Lost to follow-up is defined by the inability to reach the subject after a minimum of 2 documented phone calls, faxes, or e-mails as well as lack of response by the subject to 1 registered mail

letter. All attempts should be documented in the subject's medical records. If it is determined that the subject has died, the site will use locally permissible methods to obtain the date and cause of death. If the investigator's use of a third-party representative to assist in the follow-up portion of the study has been included in the subject's (legally acceptable representative/parent(s) or legal guardian, as applicable) informed consent, then the investigator may use a sponsor-retained third-party representative to assist site staff with obtaining the subject's contact information or other public vital status data necessary to complete the follow-up portion of the study. The site staff and representative will consult publicly available sources, such as public health registries and databases, in order to obtain updated contact information. If, after all attempts, the subject remains lost to follow-up, then the last-known-alive date as determined by the investigator should be reported and documented in the subject's medical records.

Subjects may withdraw from the study at any time at their own request, or they may be withdrawn at any time at the discretion of the investigator or sponsor for safety (see also the [Withdrawal From the Study Due to Adverse Events](#) section) or behavioral reasons, or the inability of the subject to comply with the protocol-required schedule of study visits or procedures at a given study site. Subjects that discontinue study treatment will remain in the study and must have their end of treatment visit within 1 week after their last dose, and will then enter the 4 week follow up period with an End of Study visit 4 weeks after End of Treatment visit. See [Appendix 4](#) for Guidelines for Monitoring and Discontinuation.

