### **9.2.3. Analysis of the Primary and Key Secondary Endpoints**

The primary analyses for both endpoints will be based on the FAS-RA subset. Secondary analyses will be based on the PPAS. For analysis of the primary and key secondary endpoints, a combination of graphical and analytical methods will be used. The time (in weeks) to protocol-defined flare will be used to evaluate the primary endpoint while the time (in weeks) to achieve an IGA score of  $\geq 2$  will be used to evaluate the key secondary endpoint. Subjects who do not report an event (ie protocol-defined flare or IGA  $\geq 2$ ) or discontinue the study during the double-blind randomized period will have their time to event censored at their last known visit in this period. Kaplan-Meier curves will be used to display the time to event and report the median time to event (and its 95% confidence interval) among the three randomized groups. The log-rank test will be used to compare these curves. Proportions of subjects with an event and confidence intervals will also be reported by randomized group.

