5.2.4. Analyses for Time to Event Data

For all time to event analyses, an origin and an accrual period will be defined (see table below), depending on the analysis populations. For a subject who experiences the event, the time to event will be the study day (relative to the origin being used for the analysis) corresponding to the actual date of the event or the earliest visit date at which the subject has already experienced the event. For all subjects who have not experienced the event and reached the end of the accrual period, their time to event will be right censored at the end of the accrual period. For subjects who permanently discontinue before the end of the accrual period without experiencing the event, their time to event will be considered missing data (see [Section 5.3.3](#) for handling of missing data in analysis).

	Origin	End of the Accrual Period
FAS-OL	Study Baseline	Last dose of open-label, run-in treatment
FAS-RA	First dose of randomized treatment	Last dose of randomized treatment
FAS-RE	Rescue Baseline	Last dose of rescue treatment

Time-to-event endpoints will be summarized using the Kaplan-Meier method and estimated survival curves will be displayed graphically. Graphs will describe the number of patients at risk over time. The median, quartiles and probabilities of not having an event at particular points in time will be estimated by the Kaplan-Meier method and their 95% CIs will also be provided when the data allows for their calculation. For some analyses, treatment differences between the probabilities of not having the event may be reported. Wald-type CIs for such differences will be reported using standard errors for the probabilities based on Greenwood's formula.

The log-rank test (stratified using age group [adults and adolescents] and disease severity [moderate and severe] at Study Baseline) p-value will be used for comparing time to event data between treatment groups.

For some analyses, a Cox regression model will be fit with treatment, age group and disease severity at Study Baseline as covariates. The estimated hazard ratio for the three pairwise treatment comparisons and its 95% CI will be reported from this model. For subgroup analyses, we will only have fixed effect of treatment in the model.

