6.1. Primary Endpoint

6.1.1. Loss of Response

6.1.1.1. Primary Analysis

- Summary: Time to loss of response (or protocol-defined flare) as measured from date of first dose of randomized treatment until the date of protocol-defined flare as recorded on the CRF.
- Population: FAS-RA.
- Statistical Method: Analyses for Time to Event Data in [Section 5.2.4](#). Probabilities of not having had the event will be reported at Week 52. Pairwise differences in these probabilities between treatments and their 95% CIs will also be reported. Hazard ratios and their 95% CIs will also be reported.
- Missing Data: See [Section 5.3.3](#).

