6.2. Key Secondary Endpoint

6.2.1. Loss of Response Based on the IGA Score

6.2.1.1. Primary Analysis

- Summary: Time to loss of response based on achieving IGA ≥ 2 (for the first time) as measured from date of first dose of randomized treatment until the last dose of randomized treatment (if not entered rescue) or first day of rescue treatment (if entered rescue).
- Population: FAS-RA.
- Statistical Method: Analyses for Time to Event Data in [Section 5.2.4](#). Probabilities of not having had the event will be reported at Week 52.
- Missing Data: See [Section 5.3.3](#).

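### Protocol and SAP censor dropouts on different dates; the SAP's last-dose rule credits unassessed time as event-free and shuts out some post-dose IGA ≥2 findings

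*SAP*

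**What the plan says.** **Protocol 9.2.3** (and the protocol summary): for both time-to-event endpoints, subjects without an event and subjects who discontinue "will have their time to event censored at their last known visit in this period".

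**SAP 5.3.3** first sets the scope: "Subjects who permanently discontinue before the end of their accrual period without experiencing the event of interest will have their event times considered missing". Its rule in the main analysis is then that "these missing event times will be considered as right censored (censored at random) on their last date of dosing".

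**SAP 5.2.4** ends the FAS-RA accrual period at "Last dose of randomized treatment". It dates an event by the study day "corresponding to the actual date of the event or the earliest visit date at which the subject has already experienced the event".

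**SAP 6.1.1.1** (flare) measures time from first randomized dose "until the date of protocol-defined flare as recorded on the CRF". That sentence has no last-dose limit.

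**SAP 6.2.1.1** (IGA ≥2) measures "until the last dose of randomized treatment (if not entered rescue"), or until the first day of rescue for those who enter it.

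**Protocol 6.6**: subjects who stop study treatment "must have their end of treatment visit within 1 week after their last dose". Protocol 6.3.5 has IGA and EASI scored at that EOT/ET visit and flare assessed there.

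**The concern.** A dropout's censoring date decides how long that subject stays in the risk set and whether a late finding can count. Two documents give two dates for the same endpoints in the same population, so the result depends on which one the programmer follows.

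The endpoints are observed only when someone scores EASI and IGA. A dosing date carries no such information, so censoring on it can miss in two directions:

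- it can run past the last assessment and treat unobserved time as event-free;
- it can stop short of an assessment that was actually made.

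The second matters for the key secondary endpoint, and its reach is wider than that endpoint. In the testing sequence of SAP 5.1, the 200 mg versus placebo comparison on IGA ≥2 is the second step. The 100 mg primary comparison can be formally claimed only if that step succeeds.

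**Working it through.** **1. Dropout with no final visit.** Scheduled double-blind visits are Weeks 16, 28, 40 and 52, so the gaps after Week 16 are 28 − 16 = 12, 40 − 28 = 12 and 52 − 40 = 12 weeks. Take a subject last assessed at Week 28 whose last dose is in Week 39 and who is then lost. The protocol censors at Week 28 and the SAP at Week 39. The SAP counts 39 − 28 = 11 weeks as event-free with no assessment behind them. The limit is about 12 weeks, before visit windows.

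**2. IGA ≥2 first seen at EOT/ET.** Take a subject who stops drug between visits, attends the EOT/ET visit 5 days later and is scored IGA 2, with less than half of the Week 12 EASI response lost. This is not a flare, because flare needs both components, so there is no rescue entry. SAP 6.2.1.1 closed the window at the last dose, so the subject is a non-event. The protocol sets no last-dose limit, and its last double-blind visit is the EOT/ET visit. SAP 5.3.1 treats the same finding differently: for binary endpoints it imputes non-response only after the last recorded observation when that falls on or after dropout, so the score is used.

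**3. Flare.** Under protocol 5.2 the subject does not dose before the flare visit, and rescue starts that day. The last randomized dose therefore normally falls before the flare date. SAP 6.1.1.1 counts the flare on its CRF date, while the 5.2.4 table has already closed accrual. The two cannot both be applied literally.

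**4. Size.** The protocol states 94% power for a median ratio of 1.5, 200 per arm, two-sided 5%. It gives no event count, placebo median or dropout rate, so the figure can only be back-solved. With HR = 1/1.5 (exponential times) and 1:1 allocation, Schoenfeld's formula gives

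D = 4(z₀.₉₇₅ + z₀.₉₄)² / (ln 1.5)² = 4(1.960 + 1.555)² / 0.4055² ≈ 301 events

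(Freedman: 309), about 75% of the 400 subjects in a pairwise comparison. Power at D events is Φ(√D × 0.4055/2 − 1.960), which is 94.0% at 301.

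Now assume a dropout rate d, and a share f of dropouts with an event seen only after the last dose, all of them lost. Events lost = 400 × d × f:

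| Dropout d | f = 10% | f = 25% | f = 50% |
|---|---|---|---|
| 5% | 2 lost, 93.9% | 5 lost, 93.7% | 10 lost, 93.3% |
| 10% | 4 lost, 93.7% | 10 lost, 93.3% | 20 lost, 92.5% |
| 20% | 8 lost, 93.5% | 20 lost, 92.5% | 40 lost, 90.6% |

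The 94% was stated for flare, and the loss in step 2 concerns IGA ≥2, for which no power is given. The table is an upper-end illustration of scale, not an estimate for either endpoint.

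**The case against.** **The SAP might be read as discarding flares found at early termination.** A reader could infer this from the last-dose language in 5.3.3 and 5.2.4. The documents do not support it. The 5.3.3 rule covers only subjects without the event, and 6.1.1.1 takes the CRF flare date. A literal last-dose cut-off would remove nearly every flare, which is not a credible intention. What remains for the primary endpoint is the different censoring date and the clash between 5.2.4 and 6.1.1.1.

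**Few subjects are affected.** The EOT/ET procedures include giving the last blinded dose at the visit, and a request to stop made at a scheduled visit turns that visit into end of treatment. Assessment and last dose can then share a date. This stands: the IGA exclusion mainly concerns subjects who stop between visits.

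**Last-dose censoring is a legitimate on-treatment choice.** The multiple-dose half-life in protocol 1.3 is 2.8 to 5.0 hours, so a finding days after stopping may reflect withdrawal rather than loss of effect on treatment. That is a fair reason to report the analysis. It does not explain the departure from the protocol, nor the crediting of unassessed weeks.

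**The tipping-point analysis already handles informative dropout.** It is planned only for the primary endpoint (SAP 6.1.1.2), and it imputes times beyond the censoring date rather than restoring an observed finding. The supportive key secondary analysis uses the PPAS, which leaves out subjects who neither flared nor completed (SAP 4.2).

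**The SAP may modify the protocol.** It may, but SAP section 2 says major changes to the primary analysis will also appear in a protocol amendment. Amendment 5 keeps the last-visit rule, and the SAP's change table lists no censoring change. The change letter of 07 May 2020 that the SAP cites was not available for this review.

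**Conclusion.** Wrong as written: the documents contradict each other. Three statements hold on the text alone:

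- the censoring dates differ between protocol 9.2.3 and SAP 5.3.3;
- the key secondary window excludes an IGA ≥2 first seen after the last randomized dose in a subject who does not enter rescue;
- the FAS-RA accrual limit in SAP 5.2.4 conflicts with 6.1.1.1.

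The practical effect is probably small. No stated sample size, power or alpha changes, and the 93.9–90.6% range depends entirely on assumed dropout and event shares. If the affected share differed between arms, the hazard ratio could also move. The documents give no basis for a direction or size, so a claim that the primary test is biased would go too far; last-visit censoring can be informative as well. The point should be settled before unblinding because it is a contradiction in a confirmatory analysis and cheap to remove.

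**What to change.** Amend SAP 5.2.4, 5.3.3, 6.1.1.1 and 6.2.1.1 together:

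- End the at-risk period at the last double-blind EASI/IGA assessment before rescue, including the EOT/ET visit. The assessment that establishes a flare precedes the first rescue dose and so falls inside.
- Count a flare or IGA ≥2 seen at that visit as an event.
- Censor other dropouts at that last assessment. This is consistent with protocol 9.2.3 and more exact, since it names the assessment rather than the visit.
- Run last-dose censoring as a sensitivity analysis for both endpoints.

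Do not write a hard 7-day limit into the rule as things stand. The one-week limit in protocol 6.6 has to be reconciled with the dosing interruption of up to 28 days (protocol sections 3 and 5, Appendix 4), after which the EOT visit can fall more than a week after the last dose.

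The cost is SAP wording and some reprogramming, with no new data. The downside is that a few assessments made off drug enter the main analysis; the sensitivity analysis shows whether they matter.

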6. ANALYSES AND SUMMARIES

Treatment comparisons will only be displayed for the FAS-RA analysis set where it is relevant. Pairwise comparisons will be reported among the treatment groups. No treatment comparisons are relevant for the FAS-OL and FAS-RE analysis sets. Similarly, safety data displays will be by treatment group only for SAF-RA and not for SAF-OL or SAF-RE.

A summary of analyses for clinical efficacy endpoints is provided in [Appendix 1](#). Visit windows to be used for all efficacy analyses and some relevant safety analyses are detailed in [Appendix 2](#).

Efficacy and PRO data collected at the Week 16/Week 56 follow-up visits or at the Rescue Visit Week 16 follow-up visit will be displayed in listings only, and will not be part of any analyses, unless specifically noted otherwise.

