### **9.3. Safety Analysis**

The safety data will be summarized in accordance with Pfizer Data Standards. All subjects who receive investigational product (safety population) will be included in the safety analyses. All safety data will be summarized descriptively through appropriate data tabulations, descriptive statistics, categorical summaries, and graphical presentations. Safety endpoints for the study include:

- Treatment-emergent AEs and SAEs;
- Withdrawals from active treatment due to AEs;
- Serious infections, defined as any infection (viral, bacterial, and fungal) requiring hospitalization or parenteral antimicrobials or meets other criteria that require it to be classified as a serious adverse event, will be summarized;
- Safety laboratory tests (eg, hematology [including coagulation panel], chemistry and lipid profiles);
- Vital signs;
- ECG parameters if applicable.

Change from baseline on laboratory data and vital signs will be additionally summarized.

Subject listings will also be produced for these safety endpoints.

All safety data will be summarized separately for each of the following key subgroups:

- Subjects who have received at least one dose of study drug during the open label run-in period. These subjects would have a cumulative exposure to 200 mg QD PF-04965842 of up to 12 weeks;
- Subjects who have been randomized and have received at least one dose of randomized study treatment. Summaries of safety data will be reported for these subjects by randomized treatment regimen;
- Subjects who meet loss of response criteria during the randomized, double-blind period and receive at least one dose of rescue treatment. Summaries of safety data will be reported for these subjects by randomized treatment regimen.

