5.2. General Methods

In general, for descriptive analyses, number and percent will be presented for binary endpoints. Number, median, Q1 and Q3 will be presented for descriptive analyses of continuous efficacy endpoints.

For each of the analysis methods below, treatment comparisons will only be displayed for the FAS-RA analysis set where it is relevant. Pairwise comparisons will be reported among the treatment groups. No treatment comparisons are relevant for the FAS-OL and FAS-RE analysis sets.

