For analyses where treatment comparisons are not relevant, only the proportion of responders will be reported along with its 95% confidence interval based on normal approximation (or the Clopper-Pearson exact method when there are no or 100% responders).

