5.2.2. Analyses for Longitudinal Continuous Data

Mixed-effect, repeated measures (MMRM) models will be used. Fixed effects for visit, treatment group, treatment-by-visit interaction (where treatment comparisons are relevant), disease severity at Study Baseline and randomization stratification factor will be included in the model. Visit will be modeled as a categorical covariate. Unstructured covariance matrix will be assumed for the model errors. Compound symmetry covariance matrix will be used if the model with unstructured covariance doesn't converge.

When modeling the change from baseline values, the variable for visit will start with the first post-baseline visit, and the actual baseline value will be included as a covariate. At each visit, estimates of least square mean (LSM) values and the pairwise LSM differences between the treatment groups will be derived from the model. The corresponding p-values and 95% confidence intervals will also be derived from the model.

For analyses where treatment comparisons are not relevant, the MMRM model will not have treatment as a factor and only estimates of the LSM values along with their 95% confidence intervals by visit will be reported.

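### SAP 6 drops, without recording it, the rescue-period safety summaries by randomized regimen that Protocol 9.3 requires; the pooled changes from Rescue Baseline then dilute any effect of re-exposure after placebo

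*SAP*

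**What the plan says.** **Safety.** Protocol 9.3 lists three subgroups whose safety data are to be summarized separately. The third is "Subjects who meet loss of response criteria during the randomized, double-blind period and receive at least one dose of rescue treatment", and for it the protocol states: "Summaries of safety data will be reported for these subjects by randomized treatment regimen". SAP 6 states: "Similarly, safety data displays will be by treatment group only for SAF-RA and not for SAF-OL or SAF-RE". SAP 6.7.2 measures laboratory change in SAF-RE from Rescue Baseline to the end of rescue. SAP 3.4 takes Rescue Baseline as the last observation between the last blinded dose and the first rescue dose.

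**Efficacy.** SAP 5.2 states: "No treatment comparisons are relevant for the FAS-OL and FAS-RE analysis sets". For binary endpoints in such sets, SAP 5.2.1 says that "only the proportion of responders will be reported along with its 95% confidence interval based on normal approximation". For continuous endpoints, SAP 5.2.2 says that "the MMRM model will not have treatment as a factor". Protocol 9.2.4 asks that the response at the end of rescue be judged against its start. It gives no instruction to split by arm.

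**The concern.** SAP 6 treats SAF-RE like SAF-OL, but the two sets differ. Run-in subjects all receive 200 mg and have no randomized arm. Rescued subjects come from three arms and all receive 200 mg plus topical therapy. Compared with their blinded treatment, that is a re-start, a dose increase, or the same dose with topicals added.

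Protocol 1.2.4 reports dose-dependent platelet decreases that plateaued at Week 4. A renewed fall on re-exposure would be expected mainly in ex-placebo subjects. In a pooled mean it is averaged with subjects who were already on drug when Rescue Baseline was taken. If SAP 6 is followed as written, the display that the protocol promised is not produced, and the reader is not told that the plan changed.

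**Working it through.** The plan gives no figure on this point to reproduce. The first three steps compare texts. The last three are illustrations.

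**1. The two rules.**

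| Set | Protocol 9.3 | SAP 6 |
|---|---|---|
| Run-in | Summarized; one treatment only | Not by treatment group |
| Randomized | By randomized regimen | By treatment group |
| Rescued | By randomized regimen | Not by treatment group |

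The rules conflict only in the last row, and both cannot be followed.

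**2. Does another SAP section restore the protocol rule?** No. SAP 4.3 defines SAF-RE without any arm classification. SAP 6.7 says that subjects are classified by the actual regimen received, but this follows the SAF-RA text. The SAF-RE sentence after it names no arms.

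**3. Is the change recorded?** Protocol 9 allows the SAP to modify the protocol's plans where appropriate, so a departure is possible. SAP Table 1 lists the changes in version 2, and none concerns SAF-RE. Its only general entry cites clarity and alignment with the protocol, and this change moves away from the protocol.

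**4. Dilution of a safety signal.** Let s be an arm's share of the rescued set and D its mean change from Rescue Baseline. Then

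pooled change = s(placebo) × D(placebo) + s(100) × D(100) + s(200) × D(200).

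The documents give no flare rates by arm, so the shares need assumptions: exponential flare times, 40 weeks, 1:1:1 allocation with 200 per arm, every flare rescued, placebo median 8 to 30 weeks, and ratios of active to placebo median (100 mg/200 mg) from 1.5/1.5, the planning value, to 3/6. The flare probability is 1 − 2^(−40/median), and the share is that probability divided by the sum over arms.

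| Placebo median; ratios | Flare probability (placebo/100/200) | Rescued | Shares |
|---|---|---|---|
| 8 weeks; 1.5/1.5 | 0.969/0.901/0.901 | 194/180/180 | 35/32.5/32.5% |
| 30 weeks; 3/6 | 0.603/0.265/0.143 | 121/53/29 | 60/26/14% |

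These rows are the ends of the range. If D(100) = D(200) = 0, the pooled change is 35% to 60% of D(placebo). If D is the same in all arms, nothing is diluted.

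**5. Rescue efficacy, same shares, assumed response rates.** With response of 80/60/40% (ex-placebo/ex-100 mg/ex-200 mg):

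- first row: 0.350 × 80 + 0.325 × 60 + 0.325 × 40 = 60.5%, which is 20.5 points above the ex-200 mg rate;
- second row: 0.597 × 80 + 0.262 × 60 + 0.141 × 40 = 69.1%, which is 29.1 points above.

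With 70/60/50%, the pooled rates are 60.2% and 64.6%, or 10.2 and 14.6 points above the ex-200 mg rate. With equal rates the gap is zero. No document supports any of these response rates.

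**6. Precision by regimen.** At an assumed 60% response, the 95% half-width is 1.96 × √(0.6 × 0.4/n). For n = 194 it is 6.9 points. For n = 29 it is about 18 points. Display by regimen is feasible, and is least precise for ex-200 mg subjects.

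**The case against.** The SAP may modify the protocol, so the departure is not impermissible in itself. That stands. The fault is that the change is unrecorded and unexplained.

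The platelet concern is partly covered. SAP 6.7 uses Study Baseline for laboratory abnormality criteria throughout and plans subject listings. That also stands, but it leaves the mean changes and the group percentages pooled.

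A reader might infer that pooled rescue efficacy also contradicts Protocol 9.3. It does not. Section 9.3 covers safety, and Protocol 9.2.4 sets no rule by arm for rescue efficacy. The sentence in Protocol 9.2.1 about reporting by regimen or sequence follows the FAS-RA definition and precedes FAS-RE. SAP 4.1 repeats it under FAS-RA only.

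A reader might also infer that the rescue objective gets no interpretable answer. The objective is the efficacy of 200 mg combined with topical therapy in cases of flare, which is one package offered to every rescued subject. A pooled within-subject result with a confidence interval answers that descriptively.

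Nor would a split by regimen isolate the drug or the topicals. Protocol 5.2.1 has all rescued subjects start topicals on rescue Day 1, and there is no control without them. Subjects also enter rescue after randomization, on meeting a flare threshold, so regression to the mean is possible in every arm.

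**Conclusion.** The safety conflict between Protocol 9.3 and SAP 6 is certain from the text and should be corrected. Its consequence is dilution: under the assumptions shown, a change confined to ex-placebo subjects would appear at 35% to 60% of its size. The actual figure depends on flare rates that the documents do not give, and on changes in the other two arms.

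For efficacy there is no breach and no failure to address the objective. What pooling leaves unseen is whether the rescue result differs by previous arm. The gaps of 10 to 29 points between the pooled and ex-200 mg rates are illustrations under assumed response rates. They are not evidence of bias in the estimate for the package.

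**What to change.** In SAP 6, remove SAF-RE from the sets not displayed by treatment group, so that the exclusion covers SAF-OL only. State that SAF-RE is displayed by randomized regimen with a pooled total, as Protocol 9.3 says, and carry this into SAP 6.7 and 6.7.2. If the sponsor prefers pooling, the SAP should record and justify the departure, and the two documents should be reconciled.

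As an optional descriptive addition, report FAS-RE response proportions and changes from baseline by randomized regimen, with 95% confidence intervals and no p-values, beside the pooled estimate. Label them as post-randomization and descriptive.

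The cost is SAP wording and extra table columns; no new data are needed. The downside is wider intervals per regimen, most of all for ex-200 mg subjects.
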